^o At all visits, spirometry must be performed for all subjects before dosing and should be performed prebronchodilator (Section 11.6.1). At Day 1 and Day 15, subjects <18 years of age at the Screening Visit will have additional spirometry performed at 2 and 4 hours postdose. If more than 1 spirometry assessment is required at a visit, bronchodilators should be withheld until the last scheduled spirometry assessment is completed.

^p Sweat chloride collection will occur approximately 1 hour before the PK sample collection and before the morning dose of the study drugs. At each time point, 2 samples will be collected, 1 from each arm (left and right). Collection of sweat chloride will not overlap with any other study assessments.

Table 3-2 Treatment Period and Safety Follow-up Visit Assessments – VX14-661-106

Event/Assessment ^a	Day 1	Day 15 (± 3 days)	Week 4 (± 5 days)	Week 8 (± 5 days)	Week 12 (± 5 days)	Week 16 (± 5 days)	Week 20 (± 5 days)	Week 24 (± 5 days)	ETT Visit ^b	Safety Follow-up Visit 28 (± 7) days After the last dose of study drug (if applicable) ^c
Serum chemistry	X ^a	X	X	X	X	X		X	X	X
Lipid panel ^r	X				X			X	X	
Vitamin levels	X				X			X	X	
PK sampling ^s	X				X	X			X	X
[REDACTED]										
[REDACTED]										
[REDACTED]										
[REDACTED]										
[REDACTED]										
Other events related to outcome ^u	X	X	X	X	X	X	X	X	X	
Randomization ^v	X									
Meal(s) or snack(s) at site ^w	X	X	X	X	X	X				
Study drug dosing ^x	Day 1 through Week 24									
Study drug count		X	X	X	X	X		X	X	

^a Blood samples will be collected before the first dose of study drug.

^r Blood samples will be collected for the lipid panel following at least a 4-hour fast.

^s PK samples will be collected on Day 1 at predose; at Week 12 (predose, 0.5, 3, and 6 hours after the morning dose); and at Week 16 (predose, 2, 4, and 8 hours after the morning dose). At the Safety Follow-up Visit and ETT Visit, a single blood sample for PK will be collected. If study drug is not administered on the visits of Weeks 12 and 16 (i.e., study drug interruption or permanent discontinuation of study drug), only 1 PK blood sample will be collected at each of these 2 visits.

[REDACTED]

^u Other events related to outcome include assessments relating to pulmonary exacerbations, administration of antibiotic therapy for sinopulmonary signs or symptoms, and hospitalizations (Section 11.6.12).

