7. For visits after the Day 1 Visit, subjects will be instructed to bring all used and unused study drug to the site; study drug will be dispensed at each visit, as appropriate.
8. At the Week 24 Visit, the morning dose of study drug will NOT be administered. The last dose of study drug will be the evening dose administered the day before the Week 24 Visit.

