8.3.1.2 Primary Analysis of Primary Efficacy Endpoint

The primary analysis will be based on a mixed model for repeated measures (MMRM) implemented using SAS PROC MIXED with a REPEATED statement. The null hypothesis to be tested is that the mean absolute change from baseline in percent predicted FEV₁ through Week 24 is the same for TEZ/IVA and placebo. A *P* value of 0.05 or less will be interpreted as sufficient evidence to reject the null hypothesis.

The model includes absolute change from baseline in percent predicted FEV₁ at each post-baseline visit (Day 15, and Weeks 4, 8, 12, 16, and 24) as the dependent variables, and the following fixed effects: treatment, visit, treatment-by-visit interaction, sex, age group (<18 versus ≥18 years old) at Screening, baseline percent predicted FEV₁, and baseline percent predicted FEV₁-by-visit interaction. An unstructured covariance structure will be used to model the within-subject errors. If the analysis fails to converge, a compound symmetry covariance structure will be used. Denominator degrees of freedom for the *F*-test for fixed effects will be estimated using the Kenward-Roger approximation³.

The LS Mean (SE) of the overall treatment difference between TEZ/IVA and placebo in absolute change from baseline in percent predicted FEV₁ from Day 15 through Week 24 will be presented along with the 95% confidence interval and a 2-sided *P* value.

Absolute change from baseline in percent predicted FEV₁ at each visit

The LS Mean (SE) of within-treatment group change from baseline at each post-baseline visit along with the 95% CI will be estimated from the above MMRM model. The LS Mean (SE) of the treatment difference between TEZ/IVA and placebo at each post-baseline visit will be provided along with the corresponding 95% CI and p-value. The LS means (with 95% CI) at each visit will also be plotted by treatment group. In addition, the post-baseline raw values and the absolute change from baseline in percent predicted FEV₁ at each post-baseline visit will be summarized descriptively (n, mean, SD, median, minimum, and maximum). The cumulative distribution of the absolute change from study baseline in ppFEV₁ through week 24 will be plotted by treatment group.

[REDACTED]

[REDACTED]

[REDACTED]

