This analysis will be similar to that used for the primary analysis of the primary efficacy endpoint. The key difference is that this MMRM will include only the measurements up to the date of the last dose for subjects in the FAS. This analysis will use assessments taken between the first dose date through 5 days after the last dose of study drug.

Absolute change from baseline in percent predicted FEV₁ at Week 24 using ANCOVA model

For the absolute change from baseline in percent predicted FEV₁ at Week 24, an ANCOVA model, including treatment, sex, age group (<18 vs. ≥18 years old) at screening, and baseline percent predicted FEV₁ will be used to assess the treatment difference in the absolute change from baseline in percent predicted FEV₁ at Week 24. Missing percent predicted FEV₁ data will not be imputed. The LS Mean (SE) of the treatment difference between TEZ/IVA and placebo in absolute change from baseline in percent predicted FEV₁ at Week 24 will be presented along with the associated 95% confidence interval and a 2-sided *P* value.

[REDACTED]

[REDACTED]

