^{hh} The study drug should be administered every 12 hours (± 2 hours) within 30 minutes of starting a meal with fat-containing food such as a standard "CF" high-fat, high-calorie meal or snack. On days of scheduled visits, the morning dose of study drug will be administered at the site after predose assessments have been completed. The final dose of study drug will be administered the evening before the Week 24 Visit.

Table 11-2 Treatment Period and Safety Follow up Visit Assessments – VX14-661-106

Event/Assessment ^k	Day 1	Day 15 (± 3 days)	Week 4 (± 5 days)	Week 8 (± 5 days)	Week 12 (± 5 days)	Week 16 (± 5 days)	Week 20 (± 5 days)	Week 24 (± 5 days)	ETT Visit ^l	Safety Follow-up Visit 28 (± 7) days After the last dose of study drug (if applicable) ^m
Concomitant medications ⁱⁱ	X	X	X	X	X	X	X	X	X	X
Concomitant treatments and procedures	X	X	X	X	X	X	X	X	X	X
AEs and SAEs ^{jj}	Continuous from signing of the ICF and Assent (where applicable) through the Safety Follow-up Visit									

AE: adverse event; β-hCG: beta-human chorionic gonadotropin; CF: cystic fibrosis; CFQ-R: CF Questionnaire–Revised; ██████████; ECG: electrocardiogram;
ETT: Early Treatment Termination; IWRS: interactive web response system; PE: physical examination; PK: pharmacokinetic; ██████████; SAE: serious adverse
event; ██████████

ⁱⁱ All concomitant medications are collected through the Safety Follow-up Visit for all subjects. For subjects who discontinue treatment and are followed for certain efficacy assessments after the ETT Visit (see Protocol Section 8.1.4), concomitant antibiotic therapy for ‘sinopulmonary signs and symptoms’ are collected through the Week 24 Visit, as described in Protocol Section 11.6.12.1.

^{jj} SAEs that occur after the Safety Follow-Up Visit and are considered related to study drug(s) will be reported to Vertex GPS **within 24 hours** as described in Protocol Section 13.1.2.2.

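### The on-treatment FEV1 analysis has two conflicting cut-offs, and one of them removes the scheduled Week 24 spirometry of completers

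*SAP*

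**What the plan says.** Under Analysis of Other Secondary Efficacy Endpoints (Section 8.3.2.2.3), the SAP adds an on-treatment analysis of absolute change in percent predicted FEV1 through Week 24. It is described as similar to the primary analysis, and the difference is stated in two consecutive sentences. One stops the data at the final dose: "this MMRM will include only the measurements up to the date of the last dose for subjects in the FAS". Its immediate successor instead allows a short period beyond that dose, in these words: "This analysis will use assessments taken between the first dose date through 5 days after the last dose of study drug".

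The primary model that it follows (SAP Section 8.3.1.2) takes the change at each post-baseline "visit (Day 15, and Weeks 4, 8, 12, 16, and 24) as the dependent variables", and its headline result is the treatment difference averaged over those visits.

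The end of dosing is fixed relative to the last visit. Protocol Section 10.2 rules out a dose on the day of the Week 24 Visit and adds: "The last dose of study drug will be the evening dose administered the day before the Week 24 Visit". The SAP repeats this in a footnote to its own schedule (Section 11.1, Table 11-2).

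**The concern.** The two sentences define different datasets for one model. The word *only* in the first prevents reading the second as an addition to it. The SAP's rule that it prevails over the protocol (Section 3) does not help, because both sentences are in the SAP.

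The gap between the rules is only 5 days, but it contains a scheduled assessment. No dose is given on the day of the Week 24 Visit, so Week 24 spirometry in a completer always comes after the last dose. Read literally, the first rule removes Week 24 from an analysis whose title says it runs through Week 24. The result would in effect cover Day 15 to Week 16. It could not be set beside the primary estimate as the same quantity under a different treatment-adherence restriction.

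Two programmers each following one sentence would build different datasets. The cut-off should be settled before unblinding.

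**Working it through.** The plan gives no figure to reproduce here, so the check is date logic followed by a count.

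**Inputs**

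- Rule A: keep a measurement if its date is on or before the last dose date (SAP 8.3.2.2.3, first sentence).
- Rule B: keep it if its date is on or before the last dose date + 5 days (SAP 8.3.2.2.3, second sentence).
- Last dose = day before the Week 24 Visit (Protocol 10.2; Protocol Table 3-2 and SAP Table 11-2 footnotes).
- Spirometry is scheduled at Day 15 and Weeks 4, 8, 12, 16 and 24, with target days 15, 29, 57, 85, 113 and 169 (SAP 11.2).
- Week 24 Visit window ±5 days, that is Days 164 to 174. The Week 24 analysis window for spirometry is Days 142 to 183 (SAP 11.2).

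**Step 1: does the Week 24 value survive?** Let V be the day of the Week 24 Visit, so the last dose is on V − 1.

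- Rule A needs V ≤ V − 1, which is never true.
- Rule B needs V ≤ (V − 1) + 5 = V + 4, which is always true.

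V cancels, so the visit window makes no difference: for all 11 days from 164 to 174, A excludes the value and B keeps it.

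| Nominal case, last dose Day 168 | Last day kept | Scheduled visits kept |
|---|---|---|
| Rule A | Day 168 | 15, 29, 57, 85, 113 (5 of 6) |
| Rule B | Day 173 | 15, 29, 57, 85, 113, 169 (6 of 6) |

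**Step 2: how many values?** Each completer dosed per protocol loses 1/6 = 16.7% of scheduled post-baseline values under A and none under B. The documents give no treatment-stop rate, so a range is assumed. The planning dropout figure of 10% is used only as its middle value.

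| Assumed share stopping treatment | Week 24 values excluded, no missed visits | With 10% of Week 24 visits missed |
|---|---|---|
| 5% | 490 × 0.95 = 465.5 | 465.5 × 0.90 = 419.0 |
| 10% | 490 × 0.90 = 441 | 441 × 0.90 = 396.9 |
| 20% | 490 × 0.80 = 392 | 392 × 0.90 = 352.8 |

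**Step 3: what would remain at Week 24 under A?** Only stray records in Days 142 to 183 dated on or before the last dose: unscheduled spirometry, visits with a dosing deviation, or a late early-termination reading taken on the last-dose date (SAP 8.1 maps early-termination assessments to regular visits).

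**Step 4: effect on the averaged estimate.** Let *a* be the mean treatment effect over the first five visits and *b* the Week 24 effect.

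- Six-visit average: (5a + b)/6
- Five-visit average: a
- Difference: a − (5a + b)/6 = (a − b)/6

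That is 0.17 percentage point per 1-point gap between a and b, and zero if the effect is constant. It is exact only if Week 24 leaves the model. If a few stray records keep the level in, the average still nominally covers six visits, but its Week 24 part is very poorly estimated. The unstructured covariance may then fail to converge and trigger the compound-symmetry fallback in SAP 8.3.1.2.

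**Step 5: early discontinuers.** The rules also differ for anyone with spirometry 1 to 5 days after the last dose. Using target days alone, this applies to 29 of the 167 possible last-dose days from Day 1 to Day 167, before counting early-termination visits.

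**The case against.** The best reply is that the intent is clear enough. The first sentence can be read as a loose description of how this analysis differs from the primary one. The second is the working rule: it alone gives both a start and an end, and it alone fits the title and the primary model's visits. A programmer who applied the first would soon notice a nearly empty Week 24 level and ask. That is plausible, and the fix adopts the same reading. It does not settle the point, because the visible text never says that the second sentence governs, and the first is worded as a restriction.

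The reach is also limited. The analysis is not among the secondary endpoints listed in SAP Section 5.1.2 and is outside the testing hierarchy in Section 8.3.2.2.2. The primary model is not restricted by last dose, and Week 24 is also estimated by a separate ANCOVA. This stands in full and sets the weight of the point.

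The size in Step 4 has no anchor in the documents. They give no expected gap between Week 24 and earlier visits, and Protocol Section 8.2.1 expects a response within 14 to 28 days, so the gap may be small. This also stands: the one-sixth figure is a conversion factor, not a forecast. Finally, some SAP text near these sections is blacked out, so the statement that nothing resolves the conflict covers the visible text only.

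**Conclusion.** The point holds. The SAP gives one analysis two incompatible end dates. The first excludes the scheduled Week 24 spirometry of every completer dosed per protocol, whatever day in the visit window the visit falls on. This rests only on the documents' own dosing and visit rules.

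Under that rule 1 in 6 scheduled values per completer is lost. That is roughly 350 to 470 Week 24 values in all, under assumed treatment-stop rates of 5% to 20% and 0% to 10% missed visits. The change in the averaged effect is unknown and could be zero. The certain consequence is that the table would not describe what its title says and would not be comparable with the primary result. The harm is confined to this supportive analysis, but it should be corrected before data lock because the fix is simple and leaves no choice to be made after unblinding.

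**What to change.** In SAP Section 8.3.2.2.3, remove the clause that ends the data at the date of the last dose and merge the two sentences into one. For example: the key difference from the primary analysis is that the model uses, for subjects in the FAS, only assessments from the first dose date to 5 days after the last dose, inclusive. This keeps all six scheduled visits for completers and gives one rule for early discontinuers and early-termination readings.

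The cost is one sentence. The 5-day rule is already in the SAP, no further data are needed, and no other analysis changes.

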8.4 Safety Analysis

All safety analyses will be based on the Safety Set. Subjects will be analyzed according to the treatment they actually received if they took the same study drug during the entire study period. For subjects receiving study drug from more than one treatment group by error, the treatment group allocation will be TEZ/IVA.

The overall safety profile of study drug will be assessed in terms of the following safety and tolerability endpoints:

- Adverse events
- Clinical laboratory values (hematology, serum chemistry, coagulation studies, vitamin levels, lipid panel, and urinalysis)
- Standard 12-lead electrocardiograms
- Vital signs
- Pulse oximetry
- Postdose ppFEV₁ and FEV₁ (L) and change from predose.

Safety endpoints will be analyzed using data during the treatment emergent period. Only descriptive summaries will be presented and no statistical testing is planned.

Treatment Emergent (TE) Period will include the time from the first dose of study drug to the Safety Follow-up Visit, or to 28 days after the last dose of the study drug for subjects who do not have a Safety Follow-up Visit, or to the last study participation day (i.e., the day right before the first study dose in the extension study for subjects who enrolled into the extension study), whichever occurs first.

For the purpose of safety analyses, the entire study period will then be further divided into 3 segments:

- The **pre-treatment period** is the period after the informed consent/assent date and before the start date of the TE period.
- The **treatment-emergent period** (TE period) is defined as above.
- The **post-treatment period** is the period after the end of the TE period to the date of the last study record in the clinical database.

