8.1.3 Follow-up

The Safety Follow-up Visit assessments are listed in Table 3-2. There will be an outpatient Safety Follow-up Visit approximately 28 (\pm 7) days after the last dose of study drug for subjects who complete study drug dosing and for subjects who prematurely discontinue study drug dosing.

The Safety Follow-up Visit is not required for subjects who complete the Week 24 Visit and have enrolled in an extension study of VX-661 in combination with ivacaftor within 28 days after the last dose of study drug.

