13.1.1.3 Documentation of Adverse Events

All AEs will be collected from the time ICF is signed until the following time points:

- For subjects who do not enroll: until time of screen failure (e.g., screen failure, withdrawal of consent)
- For enrolled subjects who have a Safety Follow-Up Visit: through the Safety Follow-up Visit
- For enrolled subjects who do not have Safety Follow-up Visit, through the earliest of
 - 28 days after the last dose of study drug,
 - the ETT Visit, if that visit is 3 weeks or later after the last dose of study drug (Section 8.1.4)
 - prior to the first dose of study drug in the extension study.

All subjects will be queried, using non-leading questions, about the occurrence of AEs at each study visit. When possible, a constellation of signs and/or symptoms will be identified as 1 overall event or diagnosis. All AEs for enrolled subjects will be recorded in the CRF and source document. AEs for subjects who are screened but not subsequently enrolled in the study will be recorded only in the subject's source documents. The following data will be documented for each AE:

- Description of the event
- Classification of “serious” or “nonserious”

- Date of first occurrence and date of resolution (if applicable)
- Severity
- Causal relationship to study drug(s)
- Action taken
- Outcome
- Concomitant medication or other treatment given
- Indication of dose limiting toxicity

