8 STATISTICAL ANALYSIS

8.1 General Considerations

All individual subject data in the All Subject Set will be presented in data listings. The Schedule of Assessments is provided in Section 11.1. The precision standards are provided in Section 11.6.

Continuous variables will be summarized using the following descriptive summary statistics: the number of subjects (n), mean, standard deviation (SD), median, minimum value (min), and maximum value (max).

Categorical variables will be summarized using counts and percentages.

Baseline Value, unless otherwise specified, is defined as the most recent non-missing measurement (scheduled or unscheduled) collected prior to or on the first dose of study drug. For ECGs, the baseline will be defined as the average of the 3 pre-treatment measurements (triplicate) on Day 1. For sweat chloride, the baseline value will be the mean of last assessment values on the left and the right arm prior to the first dose of the study drug.

Change (Absolute Change) from baseline will be calculated as Post-baseline value – Baseline value.

Relative change from baseline will be calculated and expressed in percentage as $100 \times (\text{Post-baseline value} - \text{Baseline value}) / \text{Baseline value}$.

Treatment Emergent (TE) Period will include the time from the first dose of study drug to the Safety Follow-up Visit, or to 28 days after the last dose of the study drug for subjects who do not have a Safety Follow-up Visit, or to the last participation date in the study (i.e., the day right before the first study dose in the extension study for subjects who enrolled into the extension study), whichever occurs first. The TE period will be used for safety analyses unless otherwise specified.

Unscheduled Visits: Unscheduled visit measurements will be included in the following:

1. derivations of measurements at scheduled visits per specified visit windowing rules below;
2. derivations of baseline/last on-treatment measurements;
3. derivations of the maximum/minimum on-treatment values and maximum/minimum changes from baseline values for safety analyses;
4. data listings where appropriate.

Visit Windowing Rules: Section 11.2 defines the windows for protocol-defined visits. The windows will be applied using the following rules for both scheduled and unscheduled visits:

1. If no measurement is available within a visit window, the assessment will be considered missing for the visit;

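### The treatment-emergent period ends the day before the first extension dose, so Week 24 Visit safety data drop out of the SAP 8.4 summaries for any subject who starts the extension on the visit date

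*SAP*

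**What the plan says.** SAP 8.1 and 8.4 give the same definition. The TE period starts at the first dose and ends at the earliest of three points: the Safety Follow-up Visit; 28 days after the last dose if there is no such visit; and the end of participation, which SAP 8.4 explains as "the day right before the first study dose in the extension study for subjects who enrolled into the extension study". SAP 8.1 words the third point almost identically. Both sections express it as a day, not as a time.

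The TE period decides which safety data are summarised. SAP 8.4 states: "Safety endpoints will be analyzed using data during the treatment emergent period". SAP 8.1 adds: "The TE period will be used for safety analyses unless otherwise specified". What comes later belongs to the post-treatment period, which "is the period after the end of the TE period to the date of the last study record in the clinical database".

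On dosing, Protocol 10.2 (item 8) withholds the Week 24 morning dose: "The last dose of study drug will be the evening dose administered the day before the Week 24 Visit". On rollover, Protocol 8.1.3 waives the Safety Follow-up Visit for subjects who complete Week 24 and "have enrolled in an extension study of VX-661 in combination with ivacaftor within 28 days after the last dose of study drug". Neither document gives a minimum gap or a date for the first extension dose.

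The protocol draws the line elsewhere. Its TE definition (12.3.1) has no extension cut-off. Its adverse event (AE) collection period (13.1.1.3), for subjects without a Safety Follow-up Visit, has as one of its end points "prior to the first dose of study drug in the extension study". SAP Section 3 says that the SAP governs where its methods differ from the protocol's.

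**The concern.** The Week 24 Visit is the end-of-treatment safety assessment. If the extension starts on that date, the predose samples and recordings are taken in this study, after about 24 weeks of exposure and before any extension drug. The day-level cut-off still dates them after the TE period. They would be missing from the laboratory, ECG, vital sign and oximetry summaries, including the threshold and liver-test shift tables. An AE starting that morning would be classed as post-treatment and left out of the TE adverse event tables.

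The SAP does not seem to intend this. Section 11.2 maps safety data to Week 24 with a target of Day 169. Section 8.4.2 plans a vitamin and lipid shift table to Week 24. Section 8.4.1.8 has an AE interval that opens on Day 169. The TE rule can remove the data that these outputs need.

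**Working it through.** **Inputs**

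- Study-day convention (Protocol Section 3): Week k falls on Day 7k + 1. The protocol's own example, Week 8 = Day 57, is reproduced: 7 × 8 + 1 = 57. Week 24 = 7 × 24 + 1 = Day 169, the target day in SAP 11.2. Week 16 = 7 × 16 + 1 = Day 113.
- Week 24 Visit window: ± 5 days, so Days 164 to 174.
- Last dose day L = V − 1, where V is the Week 24 Visit day (Protocol 10.2).
- First extension dose day E: not given. Assumption: E = V + g, with g = 0 or more.

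**Formulas for a rollover subject without a Safety Follow-up Visit**

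- SAP TE end = min(L + 28, E − 1)
- Protocol 12.3.1 TE end = L + 28
- Week 24 data are inside the TE period if V ≤ TE end.

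**Results**

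| Visit day V | Last dose L | Gap g | First extension dose E | SAP TE end | Week 24 inside? | Protocol TE end |
|---|---|---|---|---|---|---|
| 164 | 163 | 0 | 164 | 163 | No | 191 |
| 169 | 168 | 0 | 169 | 168 | No | 196 |
| 174 | 173 | 0 | 174 | 173 | No | 201 |
| 169 | 168 | 1 | 170 | 169 | Yes | 196 |
| 169 | 168 | 7 | 176 | 175 | Yes | 196 |

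With g = 0 the visit always falls one day outside. With g of 1 or more it stays inside. The protocol definition keeps it in every case shown. In the Day 169, g = 0 case, the AE interval that opens on Day 169 would close on Day 168, so it contains no days.

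**What a same-day starter loses from the TE-based 8.4 summaries** (visits from Protocol Table 3-2)

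- Chemistry, hematology, ECG, vital signs and oximetry are scheduled at Day 15 and Weeks 4, 8, 12, 16 and 24. One of these six post-baseline visits is lost. The last scheduled TE value is Week 16: 168 − 113 = 55 days before the last dose at target days.
- Coagulation after Day 1 is scheduled only at Week 24, the Early Treatment Termination Visit and the Safety Follow-up Visit. A completer has no early termination visit, and the follow-up visit is waived on rollover. No TE post-baseline value is scheduled.
- Vitamins and lipids keep Week 12 but lose Week 24, unless the shift table in SAP 8.4.2 is read as an exception to the TE rule.

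**What is not lost**

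- The spirometry decline summaries in SAP 8.5.1, which are by visit, and the weight and BMI summaries in SAP 8.5.2, which run through Week 24.
- The Week 24 eye examination when it is done earlier; Protocol 11.7.8 allows up to 4 weeks before the visit.
- Individual data listings (SAP 8.1).
- A Week 24 value supplied by an unscheduled test inside both the visit window and the TE period.

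**How many subjects.** The share s of rollover subjects with g = 0 is not in the documents; its range is 0 to 1. For scale, 245 randomized per arm with the planned 10% dropout leaves 245 × 0.90 = 220.5, about 220 per arm. That is the ceiling if every non-dropout completes treatment, rolls over and starts on the visit date. The floor is zero.

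**The case against.** The strongest objection is that the loss depends on an extension schedule that the documents do not contain. If every subject starts at least one day after the Week 24 Visit, nothing is lost. This stands: the size is unknown and may be zero. The wording still allows the failure, and no text exempts predose Week 24 data.

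A reader might infer that every Week 24 safety assessment is lost, or that the Week 24 summaries would rest on a selected minority who did not roll over. The documents support neither. The SAP 8.5 summaries, earlier eye examinations, listings and unscheduled values survive, and rollover subjects who start later keep their Week 24 data.

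A harmonising reading is also available. The SAP's term is the last day of participation, and a subject attending Week 24 is participating that day. The TE rule yields where an analysis specifies otherwise, which could rescue the vitamin and lipid table. This stands in part. But the SAP defines that last day as the day before the extension dose, so for a same-day starter the term and its definition give different dates. The sections on laboratory values, ECG and vital signs repeat the TE limit rather than relax it.

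AEs that start on the visit date are not lost altogether: they become post-treatment AEs, which Protocol 12.3.4.1 lists. The AE items in Protocol 13.1.1.3 include a date of onset but no time, so an event cannot be placed before or after a dose on the same date. That stands, and it means that AEs need an attribution rule as well as a new cut-off.

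Finally, these outputs are descriptive, and SAP 8.4 plans no statistical testing of safety. That limits the severity.

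**Conclusion.** The rule is wrong as written, with a conditional effect. For any subject first dosed in the extension on the Week 24 Visit date, the TE period ends one day before the visit. The visit-date laboratory, ECG, vital sign and oximetry data then leave the TE-based summaries in SAP 8.4. This conflicts with the SAP's own Week 24 windows and outputs, and with Protocol 12.3.1 and 13.1.1.3, over which the SAP takes precedence.

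Per affected subject, one of six scheduled post-baseline visits is lost for most safety measures. About 55 days of dosing pass after the last scheduled TE liver test and ECG, and no TE post-baseline coagulation value is scheduled. The day counts assume visits at their target days, and the monitoring gap assumes no unscheduled tests.

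The number affected lies between none and all rollover subjects; the sponsor can settle it from the extension schedule. No efficacy result or hypothesis test is involved. This should be fixed before data lock and unblinding, but it does not threaten the trial's main conclusions.

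**What to change.** In SAP 8.1 and 8.4, replace the day-before cut-off. For rollover subjects, let the third end point be the first extension dose itself, and keep the existing earliest-of rule. State that all Week 24 Visit assessments taken before that dose are treatment-emergent in this study.

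Add one attribution rule for AEs whose onset date is the date of the first extension dose and whose time is not recorded. For example, count as treatment-emergent in this study any AE recorded in this study's database with that onset date.

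The cost is a sentence on the cut-off in two sections, the AE rule and one changed derivation. No new data are needed. The small downside is that an AE known only by date may be attributed to this study although it began after the extension dose. Making the change before unblinding avoids a later choice about which end-of-treatment safety data count.
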